#### **1.10 DATA MANAGEMENT:**

We appreciate the challenges associated with the organization, execution, management, and analysis of a study of this kind and recognize the importance of frequent communication between staff, students, analysts, and investigators. Protection of subject privacy and safety, meticulous data quality checks, and prudent organization is the bedrock for success of a study like this, which will require a sizeable team/staff.

IT staff will control permissions to the database to ensure proper access and data management by staff, students, and investigators. We will store and link all behavioral and assay data on a HIPPA secure cloud-based server (REDcap).

The data forms in REDcap are similar to the actual paper version of the forms that will be completed by participants and staff. All participant data will be stored and archived on a secure server at the University of Pittsburgh. The server is set for safe mode that allows two copies of each data to be saved on the server. By having the data base on REDCap, all data is secure is case of a natural disaster in which the server would be completely undamaged.

Missed Visits: All outcome collection must be reported and stored in the database. Therefore, if an outcome visit is missed or not collected, a missed visit form must be completed in REDCap. Once a missed visit form is completed, the data management team will indicate in the database that the outcome data for the specific measure is missed to follow up. All missing data in the database will require additional documentation regarding whether the data are "lost to follow up" or have been collected but there was a problem with it.

The missed visit form has three sections that must be completed:

- Time-point of the missed visit
- Outcome that was missed
- Reason the outcome was missed

If a study participant misses multiple outcome measures during the same time point, one missed visit form can be completed if the reason missed is the same for each measure. Thus, staff do not have to complete a new form for each missed outcome for the same time point. If this study participant would also miss post intervention visits, a new form must be generated since this is a different time point.

#### 1.11 QUALITY CONTROL:

There will be multiple layers to the quality control process. First, we will have double entry for all paper-pencil assessment measures that need entered into REDCap to ensure that data is entered correctly. A separate person will review the data for any discrepancies. Before randomization will occur, the study coordinator will check all data for completeness and quality. At which point, the study coordinator will complete the data management quality checklist and give approval for randomization to occur. At weekly meetings the data will be reviewed to identify any issues with QC.

#### 1.11.1 MRI QUALITY CONTROL:

Research associates (RAs) trained in MRI data acquisition and administration of tasks as well as placement of physiological equipment (e.g., blood pressure cuff) will be present at every scan. These RAs will be accompanied by another research staff member to assist in participant instruction and monitoring of physiological data during the scan. A trained MRI technician from the BRIDGE Center will be present to operate the MRI scanner and Siemens software, orienting all field of view maps and ensuring proper slice placement. Data acquired in the MRI scanner will be distributed to the [name] and [name] labs in parallel for simultaneous quality checks and maintenance of copies of original data. Data will enter a quality check pipeline that includes 4 quality control steps: (a) checking of correct image acquisition parameters, (b) an assessment of image quality parameters (i.e., signal-to-noise, contrast-to-noise, etc.), (c) an evaluation of appropriate slice orientation and brain coverage for each sequence, and (d) preprocessing to ensure minimal movement in fMRI scans.

### 1.11.2 ACTIGRAPHY, FITNESS, EMA, CARDIOVASCULAR QUALITY CONTROL:

All actigraphy, fitness, EMA, cardiovascular assessments, and questionnaires will be interrogated at baseline before randomization to confirm data quality (including means, standard deviations, out of range values, etc.). Quality control assessments will continue on a bi-weekly basis and values will be reported to the Principal Investigator for possible discussion during weekly project meetings.

#### 1.12 **RESOURCE SHARING:**

#### 1.12.1 DISSEMINATION PLAN:

First, the trial will be registered at ClinicalTrials.gov after formal approval of the protocol by the Data Safety and Monitoring Board, which is expected to be confirmed within the first 6 months of funding. Once the protocol is approved by ClinicalTrials.gov, updates to recruitment and status of the project will be provided to NHLBI every 3 months, or more frequently if requested, until the closure of the study. Finally, results from the primary and secondary aims will be uploaded to ClinicalTrials.gov within 12 months of the completion of the clinical trial. [name] has significant experience working with ClinicalTrials.gov in other clinical trials and will be responsible for seeing that these results are updated in a timely fashion.

In addition, participants will be informed of the posting of information to ClinicalTrials.gov as part of the Informed Consent process and will be informed that there will not be any individual data uploaded or any private or confidential information shared on the ClinicalTrials.gov website.

Finally, the University of Pittsburgh has internal policies in collaboration with the Human Research Protection Office (HRPO) to ensure that the registration and result reporting are in compliance with federal policy. [name] will work with the Institutional Review Board, the Data Safety and Monitoring Board, and the University HRPO to ensure that these policies are followed.

We will develop an extensive dissemination plan and will publicize the results of the study to practicing clinicians, policy makers, research study participants and the general public by utilizing diverse strategies outlined below. Dissemination will occur through the following techniques: (a) media coverage through press releases and interviews targeted to local and national newspapers, television and radio outlets; (b) production of a research summary document and "facts sheet" targeted to the general public which clearly and concisely summaries the key conclusions of the trial; (c) production of flyers, posters, brochures, and research briefs targeted to broad audiences; (d) study newsletters targeted to study participants; (e) utilizing our study website to share news and research findings to study participants and the public; (f) publishing the results from the trial in high impact and high quality scientific journals within 12 months of closure of the study.

The trial has created a publications policy structure that also provides guidelines to students and investigators about authorship, data analysis and accessibility approaches, etc.

#### 1.12.2 DATA SHARING:

We are familiar with the NIH policies regarding data sharing and will comply with local, state, and federal laws, such as the Privacy Rule, a Federal regulation under the Health Insurance Portability and Accountability Act (HIPAA). We will

follow the NIH data sharing guide and provide a data sharing plan to be reviewed and approved by the relevant NIA PO. Data sharing will be accomplished using mixed modes, each providing a different level of access. This will include data enclave (controlled, secure environment in which eligible researchers can perform analyses using data resources), researcher's efforts (investigator responds to data requests), and publishing articles in scientific publications. Each of these methods will require investigators to complete data request forms to document aims, procedures, and to ensure that all investigators understand the policies put into place by the study team. We propose to use **REDcap** (Research Electronic Data Capture) as a data enclave for investigators that may request access to certain data. REDcap is a secure web application for building and managing surveys and databases. It allows a streamlined process for rapidly creating and organizing databases and allows for automated exporting of data to Excel and common statistical packages (SPSS, SAS, Stata, R) as well as a built-in project calendar, a scheduling module, ad hoc reporting tools, and other features.

#### 1.12.3 DATA SHARING AGREEMENT:

The data-sharing agreement\_provides for: (1) a commitment to using the data only for research purposes and not to identify any individual human participant; (2) a commitment to securing the data using appropriate computer technology; (3) a commitment to destroying or returning the data after analyses are completed, (4) a commitment to focus on particular aims documented in the agreement, (5) a commitment to work with the Principal Investigator of the project to ensure accuracy of analyses and interpretations, and avoid errors. We will make the data available to outside investigators using a data sharing agreement after publication of the primary aims and at completion of quality control assessments and data organization. Protecting the rights and privacy of human subjects will be our first priority. The final datasets will be de-identified prior to release for sharing.

- Our original targeted sample size of 150 was re-evaluated by our study statistician ([name], Department of Biostatistics, University of Pittsburgh) with a focus on the minimal sample size needed to be sufficiently powered to test our primary hypotheses. Based on prior literature described in the grant application, we estimated effect sizes between .5 and .6 (Cohen's d) for changes in brain volume resulting from an exercise intervention. Using mixed effects modeling of the data in an intent-to-treat approach, we will have between 68-83% power to test our primary aim (hippocampal volume change) with 120 participants, which accounts for a possible 20% attrition rate. Similar effect sizes for the effects of exercise on various cardiovascular disease biomarkers have been reported (between .58 and .6). Therefore, a sample of 120 would provide us >80% power even with 20% attrition to test our hypotheses about the effects of exercise on cardiovascular disease biomarkers and mediators. In addition, we will be sufficiently powered (>80%) to test several of our secondary aims (e.g., depressive symptoms and functional brain connectivity) with a targeted sample of 120. In sum, we have determined that we will have sufficient power to test our primary aims with a reduction in the targeted sample size to 120. What is more at risk with a reduction in sample size is the statistical power for mediation analyses to test our tertiary aims (i.e., to use structural equation modeling approaches for examining mediators between changes in brain and changes in cardiovascular health markers). As such, we propose to move forward by conducting these tertiary aims on an exploratory basis.
- The power estimations described above include an attrition rate of 20%, but our current attrition rate is <10% for all participants that were not disrupted due to COVID. This suggests that the power estimations described above are likely conservative estimates.
- Our current exercise adherence and compliance rates are >90% indicating that we are successful at getting and keeping participants physically active. This is important because low adherence and compliance have a direct effect on our ability to test our hypotheses (i.e., if participants are not
- adherent then we would be unable to test our aims). In short, the exercise sessions and intervention are going well which supports our ability to test our primary and secondary aims with a smaller than originally proposed sample.
- The modified accrual rates described in our letter in December 2020 were overly optimistic at the time and proposed in view of the forthcoming public availability of vaccines and potential normalization of research conduct prior to the rise of SARS-CoV-2 variants. Unfortunately, the year 2021 in the Pittsburgh region has been marred by unanticipated challenges including variable vaccine hesitancy rates across different districts, the rise of the delta and other variants, continued illnesses

and hospitalizations, need for quarantine, reduced density of staff and participants in buildings, school and day care cancellations, etc. (see more on this below). As such, we propose to modify our accrual rates by taking advantage of a 1 year no cost extension (which was not included in our adjusted targets in December of 2020). We have worked closely with our budget office to confirm that we will have sufficient funds for a no cost extension and reducing our proposed targeted sample from 150 to 120 (30 participants or 60 sessions) will also reduce additional costs and time. This new accrual rate is more feasible given current trends in the COVID pandemic.

- There are two primary bottlenecks that we have experienced related to our lowerthan-expected accrual rate. First, our study team has experienced recent turnover in staff that were hired for recruitment and screening. This was noted by the study PI and DSMB members at the September 2nd, 2021 meeting. To address this issue, we have submitted hiring materials to the University of Pittsburgh Human Resources office to hire a new staff member who will be dedicated to advertising, screening, and recruitment for the study. We expect this individual to start in October 2021. In the interim, we will immediately have staff from other Projects and Cores assist in recruitment and screening efforts. Secondly, we have had an unprecedented number of session cancellations and participants withdrawing from the study during baseline assessment sessions (before randomization). As such, our screening-torandomization ratio is lower than anticipated which requires the study team to screen more individuals to randomize one person to the intervention. This behavior (session cancellations and withdrawing before randomization) has been observed across several ongoing studies and can be attributed to issues related to the pandemic described above (e.g., need for quarantine). We are currently working through methods to accommodate missed sessions or make participation in the trial more flexible and accommodating to the needs of the participants.
- The DSMB members noted on September 2nd, 2021 that the rate of minority recruitment is lower than anticipated. We are taking active steps to improve this rate including community advertisements in addition to our marketing strategy that we have used up until now. [name] has also been attending local farmer's markets to recruit within diverse neighborhoods in Pittsburgh, and we have a forthcoming meeting with an elected Councilperson in the Wilkinsburg district of Pittsburgh to formulate a community-based recruitment effort to reach out to a more diverse sample to meet enrollment targets. Once our new staff are hired and trained, we will be actively implementing these strategies to enhance minority recruitment. If necessary, we will pause the recruitment of non-Hispanic whites into the trial in order to focus on increasing enrollment of underrepresented minority groups.
- Lastly, as noted in the attached and updated accrual plan approved by the DSMB, we can report that we are currently 4 people lower than our randomization target as of this writing. Hence, 57 of 61 people have been randomized, which reflects 93% of the new DSMB approved randomization goal for this point in time.

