volumetrics: Our prior 6-12 month PA interventions in children, young adults, and older adults have used between 20^26 and 60^40 subjects per group with moderate-sized effects (Cohen's d) ranging between 0.30 and 0.50. Crosssectional research has supported these numbers with studies reporting significant effects of PA on brain volume with only 32 subjects and slightly larger effect sizes between 0.50 - 0.60. Even if we estimate a rather conservative effect size of 0.30, 60 participants per group is sufficient to detect differences in brain volume at 80% power. Diffusion imaging: Changes in white matter have been detected in PA interventions in as little as 6-months with only 50 subjects. In a 12-month exercise intervention, we found increased FA with only 35 subjects in each group with an estimated effect size of 0.70^28. Fewer results have been reported in midlife, but in children, effects of PA on white matter have been reported with N=25/group. Based on an estimated effect size of 0.75, we should have 90% power with 60 participants per group to test our main hypotheses as well as enough power for exploratory analyses. Connectivity: With only 65 people, we have shown that a 12-month exercise intervention is effective at enhancing functional connectivity in prefrontal-inhibitory networks. The difference between the groups for PFC connectivity was .15 with a standard deviation of .10 suggesting an effect size of 1.5 (Cohen's d). In young adults, we report similar effects with N=50 with increased functional connectivity between the anterior hippocampus and ACC. Therefore, similar to the effect sizes and power for the other neuroimaging measures, 60 participants per group should be sufficient for detecting changes as a function of the intervention with 95% power. Stress reactivity and affect: In preliminary data from the AHAB2 cohort, greater PA was associated with reduced daily life stress reactivity measured by strain (r=.23) and conflict (r=.25). In a 12-week exercise intervention in young adults with major depression scores on the Montgomery Asberg Depression Rating Scale significantly decreased from 21.8 to 4.25, and the magnitude of this decrease was correlated with increases in fitness (r=-.39). Based on these effect size data, 60 participants per group would provide us with >90% power to detect an effect on stress and affect measures. Thus, we estimate adequate power to test Aim 2. CVD markers: Prior randomized exercise interventions examining some of the same CVD risk markers proposed here (e.g., baroreflex sensitivity [BRS]) are typically between 4-52 weeks in duration with  $N=\sim10$  and  $150^{31}$ . Despite this heterogeneity, meta-analyses of exercise interventions show moderate-to-large effects on many of these outcomes (Cohen's d=.60). For example, a meta-analysis of 30 exercise interventions on multiple CVD risk markers reported an average 18 week duration with  $\sim 50$  subjects in each study ( $\sim 25/\text{group}$ ). In this metaanalysis, CRF increased by 3.04 mL/kg/min with a Cohen's d of 0.58. We expect larger effect sizes here because durations of ~1-year demonstrate larger changes in these metrics. Thus, based on prior studies and meta-analyses, we are sufficiently powered with N=150 to test for exercise-induced changes in CVD markers. Mediation: Using established empirical estimates of sample sizes needed for .80 power in bias-corrected bootstrapping analyses with moderate sized effects in both alpha and beta, it is estimated that 115 participants are needed. Thus, based on the above effect sizes for both brain and CVD markers, we are

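### The amendment's 68-83% power for hippocampal volume rests on d = .5-.6 as an intervention effect, whereas section 1.4.1 gives 0.30-0.50 for interventions; on the amendment's own convention that range yields about 31-68%

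*Combined protocol and SAP*

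**What the plan says.** The section headed Amendments in Study Protocol, which follows the reference list, justifies reducing the target sample from 150 to 120. For brain volume it states that "we estimated effect sizes between .5 and .6 (Cohen's d) for changes in brain volume resulting from an exercise intervention", and attributes this to prior literature described in the grant application. It then reports that "we will have between 68-83% power to test our primary aim (hippocampal volume change) with 120 participants, which accounts for a possible 20% attrition rate", using mixed-effects modelling under intent to treat. It concludes that "we have determined that we will have sufficient power to test our primary aims with a reduction in the targeted sample size to 120".

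Section 1.4.1 (Power, brain volumetrics) describes the evidence differently. The team's earlier 6-12 month physical activity interventions are said to show "moderate-sized effects (Cohen's d) ranging between 0.30 and 0.50". The next sentence turns to another design: "Crosssectional research has supported these numbers with studies reporting significant effects of PA on brain volume with only 32 subjects", with "slightly larger effect sizes between 0.50 - 0.60". The section then plans on the bottom of the intervention range: "Even if we estimate a rather conservative effect size of 0.30".

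Section 1.4.3 makes 12-month change in hippocampal volume the first of three primary endpoints, and the amendment calls it the primary aim.

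**The concern.** The range the amendment uses for an intervention effect coincides with the range section 1.4.1 gives for cross-sectional studies. Only its lowest value, 0.50, lies within the range section 1.4.1 gives for interventions. The amendment does not mention 0.30-0.50 or say why it was set aside.

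This power statement is the statistical ground for dropping 30 participants, for the endpoint the amendment treats as primary. If the intervention range in section 1.4.1 is the relevant one, the best case is the amendment's worst case, and the trial is described as better able to detect a hippocampal effect than its own documents support.

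A second problem does not depend on which range is right. The lower end of the stated power, 68%, is below the 80% that section 1.4.1 uses for brain volume and below the level above 80% that the amendment reports for its other outcomes. The text still calls the power sufficient.

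**Working it through.** **Inputs**

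- Target 120, attrition 20% (amendment); equal allocation (section 1.6). Analysed per arm: 120 × 0.80 / 2 = 48.
- Effect sizes: .5-.6 (amendment); 0.30-0.50 for interventions and 0.50-0.60 for cross-sectional research (section 1.4.1).
- Significance level: none is stated for the primary outcomes (.01 is given for mediation only). Two-sided .05 is assumed.

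**Formula.** Two-sample t-test with n per arm: noncentrality d × √(n/2), 2n − 2 degrees of freedom. With n = 48, √(48/2) = 4.899 and there are 94 degrees of freedom.

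**Reproducing the stated figure**

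| d | noncentrality | power | amendment |
|---|---|---|---|
| .50 | 2.449 | 67.9% | 68% |
| .60 | 2.939 | 82.9% | 83% |

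The match supports the assumed convention. Alternatives do not fit: one-sided .05 gives 78-90%, 60 per arm without attrition gives 78-90%, and .05/3 gives 51-69%.

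**Same convention, intervention range**

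| d | noncentrality | power, 48 per arm | power, 54 per arm (10% attrition) |
|---|---|---|---|
| .30 | 1.470 | 30.7% | 33.9% |
| .40 | 1.960 | 49.2% | 54.0% |
| .50 | 2.449 | 67.9% | 73.1% |

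**Effect detectable with 80% power.** d = .578 with 48 per arm and .544 with 54 per arm. Both exceed the top of the range that section 1.4.1 gives for intervention effects on brain volume.

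**Sample needed for 80% power.** About 64 analysed per arm at d = .50 and about 176 at d = .30.

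**Sensitivity to a repeated-measures gain.** If d is standardised to the cross-sectional standard deviation and baseline is adjusted for with correlation r, the effective effect is d/√(1 − r²). With 48 per arm and d = .30, power is about 39% at r = 0.5, 68% at r = 0.8 and 92% at r = 0.9. These correlations are illustrative; the documents give none.

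**The case against.** **The source may lie elsewhere.** The amendment cites the grant application, which is not among the documents and could contain other intervention data. Section 1.4.1's 0.30-0.50 describes the team's own studies in children, young adults and older adults, for brain volume in general rather than for the hippocampus in midlife. This stands. A reader might infer that the sponsor took the cross-sectional range and relabelled it, or that .5-.6 is simply wrong. The documents show that the ranges coincide, not how the figure was chosen. What they support is an unexplained conflict between two sections.

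**A mixed model may do better than a t-test.** Section 1.4.1 appeals to the added power of a within-subject approach, and it claims 80% power at d = 0.30 with 60 per group, where a plain two-sample test gives 37%. If that claim silently assumed baseline adjustment, the implied correlation would be about 0.81, and the same assumption with 48 per arm would give about 71% at d = .30. A reader might therefore be wrong to take 31-68% as the power of the trial. This stands as a limit on the figure. It does not rescue the amendment, because 68-83% equals the plain test with no such gain. Credit for a correlation has to be claimed and its value stated.

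**Attrition is lower than assumed.** The amendment reports under 10% among participants not disrupted by COVID and calls its estimates likely conservative. At 10% the intervention range moves only to about 34-73%.

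**Larger intervention effects are cited.** Section 1.4.1 quotes 0.58 to 1.5 for fitness, cardiovascular markers, diffusion imaging and connectivity. So it would be wrong to say that .58 exceeds every intervention effect cited; it exceeds those cited for brain volume.

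**The 68% is printed openly.** It is, and sufficiency is partly a matter of judgement. But the conclusion carries no qualification and is out of line with the 80% used elsewhere in the same plan.

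**Conclusion.** The point holds as an unreconciled conflict in the planning assumption. The amendment's arithmetic is correct on its inputs. The effect size it describes as an intervention effect is not supported by the intervention evidence the documents report, apart from the shared value of 0.50. Like for like, that evidence gives about 31-68% power against the stated 68-83%, or about 34-73% with 10% attrition. These figures rest on a two-sample test, an assumed two-sided .05 level and no gain from repeated measures. They are not an unconditional estimate of the trial's power. The claim of sufficient power for hippocampal volume is not warranted even on the amendment's own range, whose lower end is 68%.

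**What to change.** In the amendment, or in a dated clarifying note that leaves the approved record intact:

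1. Reconcile the effect sizes with section 1.4.1. Either cite the intervention data behind .5-.6 and explain the departure from 0.30-0.50, or restate hippocampal power over .30-.50 as about 31-68% at 120 randomised with 20% attrition.
2. Show the basis of whichever figure is kept: the test, significance level and sidedness, attrition, how d is standardised, and any assumed baseline correlation with its source.
3. Remove the statement of sufficient power as it applies to hippocampal volume.
4. State the effect detectable with 80% power: about d = .58 at 20% attrition on the amendment's convention (about .54 at 10%).

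The change is to wording and needs no change in enrolment, endpoints or procedures. The cost is a less favourable stated power, unless the sponsor can document larger intervention effects or a baseline correlation that supports the higher figure.
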